4.5. Removal of Patients

In accordance with the Declaration of Helsinki, patients have the right to withdraw from the study at any time for any reason. The Investigator and Sponsor also have the right to withdraw patients from the study. Patients may be removed from the study for the following reasons:

- Adverse reactions
- Clinical sepsis regardless of the cause
- At the request of the Investigator, MM, DSMB or Sponsor, whether for administrative or other reasons
- Protocol violation or unreliable behavior
- Termination of the study by the Sponsor

The date of and the reason for discontinuation will be recorded in the electronic case report form (eCRF).

Patients who withdraw from the study after receiving the first dose of IMP for reasons other than safety or tolerability may be replaced:

- Patients who withdraw before the Day 180 follow-up visit (primary end point) may be replaced upon consultation with the coordinating investigator and sponsor
- Patients who withdraw after the Day 180 follow-up visit will not be replaced

If a patient discontinues, all end of study visit procedures should be conducted.

If a patient is removed from the study, the date of the last dose of IMP and all observations collected up to the time of termination will be recorded on the eCRF along with the reason for termination. Scheduled safety evaluations and follow-up examinations (see Visit Schedule, Appendix A) will be conducted, if possible.

When a patient fails to return for scheduled assessments, the following efforts should at a minimum be made to contact him/her to determine a reason for the failure to return: 3 phone attempts, including the date and time, should be documented in the patient's source documents. If there is no response to the phone calls, a certified letter should be sent to the patient. After these efforts have been exhausted, a patient should be identified as lost to follow-up in the eCRF.

Patients enrolled into the Combination Cohorts who are excluded prior to receiving the first dose of IMP (teplizumab and AG019 or corresponding placebos) due to any of the criteria mentioned in Section 11.4.3.5 will be replaced. Replacement of patients will be done through the IRT. Details of this procedure are outlined in the IRT manual.

Confidentiality Statement

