5.2. Description of the cohorts

The enrollment plan is presented in Figure 1 and is described below.

5.2.1AG019 Cohorts

A total of 8 single dose patients and up to 24 repeat dose patients⁸ will be enrolled sequentially into the following AG019 cohorts:

- AG019 Cohort 1: 2 capsules per day, patients 18-40y
 - Single dose: 2 patients
 - Repeat dose: up to 6 patients⁸
- AG019 Cohort 2: 6 capsules per day, patients 18-40y
 - Single dose: 2 patients
 - Repeat dose: up to 6 patients⁸
- AG019 Cohort 3: 2 capsules per day, patients 12-17y
 - o Single dose: 2 patients
 - Repeat dose: up to 6 patients⁸
- AG019 Cohort 4: 6 capsules per day, patients 12-17y
 - o Single dose: 2 patients
 - Repeat dose: up to 6 patients⁸

A total of 2 single dose patients and up to 6 repeat dose patients⁸ will be enrolled in each open label safety cohort, designed to investigate the safety profile of AG019 administered alone.

Single dose patients

In a first stage, 2 single dose patients will be enrolled in a staggered way. Each of these patients will be treated for 1 day with AG019 (number of capsules of AG019 will correspond to the cohort these patients have been enrolled into). These patients will be followed up for a total of 4 days (Treatment day [Day 1] plus 3 additional days), after which they will have completed their study participation (Day 4).

After study completion of each single dose patient, the treating Investigator and MM will review the collected data, and if no safety concerns are identified, treatment of the next patient (i.e., the second single dose patient or the first repeat dose patient) can begin.

Each single dose patient will be offered the option of being re-enrolled as repeat dose patient, provided that no safety concerns have been identified during their participation as a single dose patient. A wash-

Confidentiality Statement

This document contains confidential information. It is intended solely for the use of the principal investigator, coinvestigators, staff, appropriate institutional review boards or ethical committees, and other required regulatory bodies.

AG019-T1D-101 CSP Final 9.0 11-Jun-2020

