⁸ 4 repeat dose patients will be enrolled per AG019 cohort. In addition, both single dose patients in each AG019 cohort will be offered the option of being re-enrolled as repeat dose patients, provided that no safety concerns have been identified during their participation as a single dose patient. Therefore, if both single dose patients agree to be re-enrolled as repeat dose patients, the maximum number of repeat dose patients per cohort will be 6.

out period of 7 days will be required before the single-dose patients can be re-enrolled as repeat dose patients, to ensure that no AG019 bacteria are present in their GI tract at the time of re-enrollment. In addition, these patients cannot be enrolled as staggered patients into the repeat dose group.

If a single dose patient wishes to be re-enrolled as repeat dose patient, all inclusion and exclusion criteria applicable to repeat dose patients should be met (including those criteria that do not apply to single dose patients).

Repeat dose patients

A minimum of 4 repeat dose patients will be enrolled per AG019 cohort. In addition, both single dose patients in each AG019 cohort will be offered the option of being re-enrolled as repeat dose patients in the same AG19 cohort, provided that no safety concerns have been identified during their participation as a single dose patient. Therefore, if both single dose patients agree to be re-enrolled as repeat dose patients, the maximum number of repeat dose patients will be 6.

Each of these repeat dose patients will be treated daily for 8 weeks with AG019. The first 2 repeat dose patients will be enrolled in a staggered way.

- After treatment of the first patient, the data collected up to the Day 7 follow-up visit will be reviewed by the treating Investigator and MM, and if no concerns are identified, the second patient will be treated.
- After the Day 7 follow-up visit of this second patient, the collected data will be reviewed by the treating Investigator and MM, and if no concerns are identified, the remaining patients will be treated.

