8.7. Reporting of Serious Adverse Events

For any SAEs, regardless of causal relationship, the Investigator must inform the Sponsor's pharmacovigilance vendor (XXX), the contract research organization (CRO) Project manager or Lead clinical research associate (CRA) as well as the Sponsor's representatives mentioned on the Contact Details page of this protocol within 1 calendar day of becoming aware of the event by mailing the completed SAE Report Form and any other pertinent SAE information to XXX as indicated on the SAE Report Form. Follow-up information collected for an initial report of an SAE must be reported to XXX within 1 calendar day of receipt by the Investigator.

XXX

Reports of any pregnancy in a patient, or partner of a patient, must also be emailed to the above mentioned email address within 1 calendar day (see Section 8.6).

The information to be recorded for SAEs should include the following:

- The onset of any new AE or the worsening of an observation documented from signature of the ICF
- The specific type of event in standard medical terminology
- The duration of the clinical event (start and stop dates)
- The severity of the clinical event
- Seriousness (SAE) criteria
- Relevant laboratory and examination results
- Dosing schedule of IMP(s)

Confidentiality Statement

- Indications and dosing schedules of concomitant medications
- Relationship of the AE to the IMP(s) as defined in Section 8.3
- Management of IMP(s) administration and other action taken to alleviate the clinical events
- Past medical and surgical history and concurrent diseases
- De-challenge/re-challenge results, if applicable
- The outcome of the clinical event
- Serious Adverse Event Recording Period

SAEs will be collected and recorded by the Investigator beginning from the signature of the ICF until the patient is withdrawn or has completed the study.

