8.8. Serious Adverse Event Follow-up Period

All patients who experience SAEs will be followed until the events resolve, stabilize, become chronic or the patients complete the study or are lost to follow-up.

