After all patients in all AG019 and Combination cohorts have completed their 6-month follow-up visit unblinding will be done and all data will be analyzed and reported. After completion of the full 12 months follow-up all additional data will be analyzed and reported separately.

More details on the analysis and presentation of study results will be provided in the statistical analysis plan (SAP). The SAP will be finalized prior to the unblinding of treatment allocation codes.

10.1.Study Endpoints

Primary Endpoint

The primary end point will be assessed by analysis of the incidence of treatment-emergent adverse events (TEAEs) collected up to the 6-month follow-up visit. A TEAE is defined as any event not present prior to the initiation of the treatment(s) or any event already present that worsens in either intensity or frequency following exposure to the treatment(s).

Secondary Endpoints

The pharmacodynamic activity of the study drug(s) will be assessed by measurement of biomarkers in blood and serum samples. Relevant parameters will be assessed, including immune markers for effect, relevant T1D parameters and relevant cytokines. Details about the analysis of the collected PD samples will be described in the SAP.

Following parameters will be assessed for analysis of systemic and local exposure to *L. lactis*:

- Presence of live L. lactis clinical strain bacteria in whole blood
- Measurable serum levels of hIL-10 and hPINS
- Presence of *L. lactis* clinical strain bacteria in fecal excretion

Safety information collected at all other time points will be assessed as secondary end points.

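### The protocol gives conflicting end points for safety data in withdrawn patients, so new SAEs after removal for harm may go uncollected

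*Protocol*

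**What the plan says.** Protocol 8.7 has SAEs collected and "recorded by the Investigator beginning from the signature of the ICF until the patient is withdrawn or has completed the study". Withdrawal is therefore an explicit end to SAE collection. The electronic diary also stops at withdrawal or completion (6.4.1).

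Protocol 4.5 lists adverse reactions and clinical sepsis of any cause among the reasons for which a patient may be removed from the study. For a removed patient, "all observations collected up to the time of termination will be recorded on the eCRF along with the reason for termination". The next sentence adds: "Scheduled safety evaluations and follow-up examinations (see Visit Schedule, Appendix A) will be conducted, if possible". The same section asks for the end-of-study procedures when a patient discontinues, and those include recording adverse events (7.3.4.4).

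Section 8 uses another limit for AEs and SAEs, *study exit*, which it does not define. It also requires an AE that the investigator considers related to study drug to be reported at any time after the study has been completed. For a patient who has had an SAE, 8.8 has the patient "followed until the events resolve, stabilize, become chronic or the patients complete the study or are lost to follow-up". Section 8.5 has a similar list for AEs. Neither names withdrawal as an end.

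The primary endpoint is the "incidence of treatment-emergent adverse events (TEAEs) collected up to the 6-month follow-up visit" (Protocol 10.1, SAP 3.1). SAP 6.6 analyses the data as they stand, apart from rules for missing dates.

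**The concern.** In a safety trial, the period over which events are collected should not depend on whether the patient was harmed. Here it can. A patient may be removed because of an adverse reaction or sepsis, and 8.7 then closes SAE collection. Section 4.5 would still like the patient to be seen, but nothing says that an SAE found at such a visit is to be recorded.

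Sites reading these sections could act differently, and a literal reading loses new events. The loss would be informative, because follow-up is shortened by the outcome being measured. The patient stays in the safety set denominator for every table. If removals for harm are more frequent on active treatment, the shortfall falls mainly there.

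**Working it through.** **1. End points for a withdrawn patient, side by side.**

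- 8.7, SAE collection: ends at withdrawal or completion.
- 6.4.1, diary: ends at withdrawal or completion.
- 8, AE and SAE recording: ends at study exit, undefined.
- 8, later related AEs: reportable after study completion; whether withdrawn patients are covered is not stated.
- 8.5 and 8.8, follow-up of AEs and SAEs: end at resolution, stabilization, chronicity, completion or loss to follow-up; withdrawal is not listed.
- 4.5, evaluations: scheduled safety evaluations continue after removal, if possible.
- 11.4.3.4, sepsis: stops study treatment and is silent on leaving the study, whereas 4.5 lists sepsis as a reason for removal from the study.

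**2. A combination-cohort patient removed on Day 12.**

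- The event that led to removal arose before withdrawal. It is recorded, and 8.5 or 8.8 continues to follow it.
- A new SAE at Day 60, judged unrelated, falls outside 8.7. The section 8 provision does not reach it because it is not judged related.
- A new SAE at Day 60, judged related, is reportable only if study completion in section 8 is taken to include withdrawal.
- Section 8.6 makes Grade 3 or higher lymphopenia a mandatory SAE when it occurs beyond the first 30 days from the start of teplizumab. Since 12 < 30, the 8.7 period closes before that window opens.

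**3. Which summaries are touched.** SAP 6.3.8 counts subjects with at least one event and also tabulates TEAEs by SOC and preferred term, by severity, by relatedness and for serious TEAEs. A patient removed because of a TEAE is already in the any-TEAE numerator, so later losses cannot change that proportion. They can lower a preferred term not yet reported, a worst severity grade, or the serious category if the first SAE comes after removal.

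**4. Size.** The plan states no figure to reproduce; the sample size is not based on statistical considerations (Protocol 10.2).

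Share of the 180-day primary window covered if 8.7 is applied literally = removal day / 180:

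- Day 12: 12/180 = 6.7%
- Day 28: 28/180 = 15.6%
- Day 56: 56/180 = 31.1%
- Day 90: 90/180 = 50.0%

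Illustration: suppose 2 of the 10 active patients in a combination cohort (2 open label + 8 randomized) are removed on Day 12. The uncovered time is 2 × (180 − 12) = 336 of 10 × 180 = 1,800 patient-days, or 18.7%. The 2-of-10 rate is an assumption. The result is an upper bound, because 4.5 asks for evaluations to continue if possible.

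Effect of one patient with an uncollected event on a patient-level proportion = 100/n: 25.0 points for n = 4, 16.7 for n = 6 and 10.0 for n = 10.

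Chance that a removed patient has a new SAE before Day 180, with an assumed full-window risk P and constant hazard h = −ln(1 − P)/180: 1 − exp(−h(180 − t)).

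- P = 5%: 4.7% for removal at Day 12, 3.5% at Day 56
- P = 10%: 9.4% and 7.0%
- P = 20%: 18.8% and 14.2%

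None of these risks comes from the documents; they show the range only.

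**The case against.** The strongest reply is that the plan already protects most of the data. Removal is permissive. The event that prompts it is recorded and followed, end-of-study procedures are done at discontinuation, and later related events have a reporting route. The specific toxicity rules (11.4.3.4 and 11.4.3.5) stop or interrupt treatment and do not end participation. No section gives 8.7 precedence over 4.5. Appendices A and B are absent from the supplied text, 11.4.3.6 is redacted, and any of them might settle the matter.

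All of this stands, and it rules out several stronger readings:

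- A reader might infer that the patients harmed most give the least safety data. The documents do not support that as a general statement, for the reasons just given.
- A reader might infer that the headline TEAE incidence is biased downward. For a patient removed because of a TEAE, the any-TEAE proportion cannot fall.
- A reader might take the 336 patient-days as an expected loss. They are lost only if none of the evaluations requested in 4.5 takes place or yields recorded events.
- A reader might extend the point to single-dose patients, whose participation ends on Day 4 while re-enrollment needs a 7-day wash-out. The wash-out is a condition for re-enrollment, not an adverse-event risk window. Its starting point is not stated, and no passage classifies events arising in between.

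What the reply does not answer is the new-onset SAE after removal. For that event 8.7 says stop, 4.5 says keep looking if possible, and section 8 helps only when the event is judged related and withdrawal counts as completion. In a first-in-human product, collection should not hang on a causality judgement.

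**Conclusion.** The point holds in a limited form. Sections 4.5, 8, 8.5, 8.7 and 8.8 do not agree on when safety data end for a withdrawn patient. Applied literally, 8.7 leaves new-onset SAEs after removal uncollected, chiefly those judged unrelated, and including late lymphopenia after teplizumab in a patient removed early. Removal can be caused by harm and SAP 6.6 makes no adjustment, so the Day 180 tables by preferred term, severity and seriousness can be understated.

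No figure in the plan changes. With cohorts this small, a single missed patient-level event would matter in those tables, but how many would be missed cannot be estimated from the documents. The conclusion assumes that sites follow 8.7 as written and that the appendices not seen do not override it. It is a correction that should be made, not a flaw that undermines the primary endpoint.

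**What to change.** - In 4.5, separate stopping IMP from leaving the study. Keep dosed repeat-dose patients in the already scheduled safety visits to Day 360, and at least to Day 180, unless consent is withdrawn, the patient is lost to follow-up or the sponsor terminates the study.
- In 8 and 8.7, collect AEs and SAEs over that whole period whether or not the patient is still taking IMP.
- Define *withdrawn* and *study exit* once, consistently with 8.5 and 8.8, and state whether the section 8 rule on later related AEs covers withdrawn patients.
- Reconcile the treatment of sepsis in 4.5 (removal from the study) with 11.4.3.4 (stopping study treatment), so that sites can tell which consequence applies to data collection.

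The rules on when treatment is stopped are left as they are. The cost is protocol wording and some extra follow-up of patients who have stopped treatment, at visits that already exist in the schedule.

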8.8. Serious Adverse Event Follow-up Period

All patients who experience SAEs will be followed until the events resolve, stabilize, become chronic or the patients complete the study or are lost to follow-up.

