Once all repeat dose patients in a cohort have had their Day 7 follow-up visit, the DSMB will review all available data from all enrolled patients in all cohorts. If no safety concerns are identified, the DSMB will formulate a recommendation to the sponsor on opening the next cohort(s) for treatment, according to the enrollment schedule outlined in Figure 1. Detailed guidelines on the recommendations to be formulated by the DSMB will be described in the DSMB Charter. A brief summary of these guidelines is included in Section 11.4.2.

All Repeat dose patients in all AG019 cohorts will be followed up for a total of 12 months (8 weeks of treatment plus 10 months of post-treatment follow-up). After the 12-month follow-up visit (Day 360) the patients will have completed their participation in the study.

5.2.2Combination Cohorts

The Phase 2a double-blind portion of the study will evaluate 2 cohorts ("combination cohorts") of 12 patients. Each patient will be administered 6 capsules daily 9 of AG019 (or placebo) for 8 weeks, in association with daily IV infusions of teplizumab for the first 12 days of the 8-week treatment period.

Confidentiality Statement

⁹ The dose of AG019 to be administered in the Phase 2a portion of the study is not yet known and will be determined by the results of the Phase 1b portion of the study. If the AG019 cohorts reveal safety concerns associated with the 6-capsule treatment, the DSMB will recommend lowering the AG019 dose in all AG019 and combination cohorts.

- Combination Cohort 1: 12 patients 18-40y to receive AG019 (6 capsules per day⁹, 8 weeks) plus teplizumab (daily infusions, 12 days), or matching placebo capsules and placebo infusions
- **Combination Cohort 2**: 12 patients 12-17y to receive AG019 (6 capsules per day⁹, 8 weeks) plus teplizumab (daily infusions, 12 days), or matching placebo capsules and placebo infusions

Within each of these combination cohorts, the first 2 enrolled patients will be treated with active treatment (AG019 plus teplizumab) in an open label fashion. Patients 3-12 will be randomized (4:1) to receive (double) active treatment or (double) placebo in a double-blind fashion. Therefore enrollment will be done as follows:

- Treatment of patient 1: Treatment with AG019 plus teplizumab
 - > Data review of all data collected up to the Day 12 follow up visit (the last day of teplizumab infusion) (treating Investigator and MM)
- Treatment of patient 2: Treatment with AG019 plus teplizumab

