8. ADVERSE EVENT REPORTING

Throughout the study, AEs will be recorded in the source documents and transcribed onto the appropriate pages of the eCRF regardless of whether the AEs are considered treatment related. All AEs with onset dates from signature of the ICF through study exit will be recorded as an AE on the eCRF. All SAEs with onset dates from signature of the ICF through study exit must be recorded following the guidelines in Sections 8.4, 8.6, 8.7, 8.8 and 8.9. Any AE that occurs at any time after completion of the study, which the investigator considers to be related to study drug, must be reported.

Conditions existing prior to screening will be recorded as part of the patient's medical history. To avoid confusion, the AE should be recorded in standard medical terminology. The Investigator is responsible for assessing the relationship of AEs to the AG019 as well as to teplizumab (Section 8.3).

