8.5. Adverse Event Follow-up Period

All patients with AEs will be followed until the event resolves, stabilizes, becomes chronic, the patient completes the study or the patient is lost to follow-up.

8.6.Serious Adverse Event Definition

In addition to classifying the AE as mild, moderate, severe, life-threatening or fatal, the Investigator should determine whether or not an AE is an SAE. The Investigator shall make an accurate and adequate report on any SAE to the Sponsor or its designee and to any IRB/IEC that has reviewed and is continuing to review the study regarding any SAEs (see Sections 8.7 and 8.9).

An SAE is defined as any AE occurring at any dose regardless of relationship to IMP that results in any of the following outcomes:

- results in death,
- is life-threatening, NOTE: The term "life-threatening" in the definition of "serious" refers to an event in which the patient was at risk of death at the time of the event; it does not refer to an event which hypothetically might have caused death if it were more severe.
- requires inpatient hospitalization or prolongation of existing hospitalization,
- results in persistent or significant disability/incapacity, or
- is a congenital anomaly/birth defect.

Medical and scientific judgement should be exercised in deciding whether expedited reporting is appropriate in other situations, such as important medical events that may not be immediately lifethreatening or result in death or hospitalization but may jeopardize the patient or may require intervention to prevent one of the other outcomes listed in the definition above. These should also usually be considered serious. Examples of such events are intensive treatment in an emergency room or at home for allergic bronchospasm; blood dyscrasias or convulsions that do not result in hospitalization; or development of drug dependency or drug abuse.

The following situations will be considered important medical events and must be reported as SAEs:

Confidentiality Statement

- 1. Grade 4 or higher lymphopenia for 7 or more days occurring in the first 30 days after the start of the teplizumab infusion.
- 2. Grade 3 or higher lymphopenia occurring anytime later than the first 30 days after the start of the teplizumab infusion.

Complications that occur during hospitalization are AEs. If a complication prolongs hospitalization, the event causing the prolongation is an SAE. Planned hospitalizations are not considered SAEs.

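### AE and SAE follow-up may stop at study completion, so no final outcome is required for serious or related events that are open, or first found, at the last visit

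*Protocol*

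**What the plan says.** **Follow-up rules.** For SAEs, Protocol Section 8.8 says: "All patients who experience SAEs will be followed until the events resolve, stabilize, become chronic or the patients complete the study", with loss to follow-up as the remaining alternative. For AEs, Section 8.5 follows patients "until the event resolves, stabilizes, becomes chronic, the patient completes the study or the patient is lost to follow-up". Neither section makes an exception for related, severe or unresolved events.

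**Completion.** For repeat-dose and combination patients, Sections 5.2.1 and 5.2.2 say: "After the 12-month follow-up visit (Day 360) the patients will have completed their participation in the study". Single-dose patients complete at Day 4 (Section 5.2.1), unless they take up the offer to re-enrol as repeat-dose patients.

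**Tests at the last visit.** The Day 360 visit includes local hematology and chemistry, infectious disease PCR and a 12-lead ECG (Section 7.3.4.4). The Day 4 visit of single-dose patients includes a local laboratory sample (Section 7.2.3).

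**What those tests can generate.** An abnormal ECG is recorded as an AE (Section 6.1), and so is a laboratory value judged clinically significant (Section 6.2). Section 8.6 makes the following a mandatory SAE: "Grade 3 or higher lymphopenia occurring anytime later than the first 30 days after the start of the teplizumab infusion".

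**Neighbouring rules.** On events with onset after completion, Section 8 says: "Any AE that occurs at any time after completion of the study, which the investigator considers to be related to study drug, must be reported". Section 8.7 collects SAEs "until the patient is withdrawn or has completed the study" and lists start and stop dates and outcome among the items to record. Section 8.6 follows a pregnancy to its outcome.

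**The concern.** Study completion is an administrative date, yet it stands in the list of stopping points on equal terms with resolution and stabilisation. The plan also schedules tests that can detect events on that very date. A result first seen then can open an AE or SAE for which the required follow-up has already ended.

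This is a first-in-human study of AG019 whose primary objective is safety and tolerability. If a Day 360 count shows late lymphopenia in a teplizumab recipient, a Day 360 PCR is newly positive, or a Day 4 sample from a single-dose patient is abnormal, the general follow-up rules would not oblige anyone to establish whether it resolved. Section 8.10.1 adds that an SAE whose relationship to AG019 cannot be excluded is reported as a SUSAR, so an expedited report could stay open by rule. At stake are the description of duration and reversibility of late events, and the protection of the patient concerned.

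**Working it through.** There is no stated figure to reproduce and no power or error-rate calculation applies. The check sets the follow-up rules beside the visit lists; the only arithmetic is differences between visit days.

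**1. Which stop applies to an event first found at the last visit?** A single abnormal value cannot by itself show resolution, stabilisation or chronicity, and the patient is not lost to follow-up. The stop that remains is completion, on the same day. Required follow-up: 360 − 360 = 0 days, or 4 − 4 = 0 days for a single-dose patient who does not re-enrol.

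**2. How long before the last visit was the preceding scheduled test (repeat-dose and combination patients)?** Inputs: Protocol Sections 7.3.3.1.5 and 7.3.4.1 to 7.3.4.4. SAP Section 6.3.9 agrees for PCR (Visits 13–16 and 19) and ECG (Visits 15 and 19, with Visit 17 on suspicion).

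| Test | Preceding scheduled test | Gap to Day 360 |
|---|---|---|
| Blood count | Day 270 | 360 − 270 = 90 days |
| Infectious disease PCR | Day 90 (none at Day 180 or 270) | 360 − 90 = 270 days |
| 12-lead ECG | Day 56 (Day 180 only on suspicion) | 360 − 56 = 304 days |

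An abnormality visible only on the test, arising within that gap, may first be found at completion. An unscheduled visit, which includes local laboratory tests and PCR (Section 7.4), could find it sooner.

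**3. Single-dose patients.** The Day 1 list (Section 7.2.2) has no blood draw, so the Day 4 sample is the only post-dose laboratory sample. For a patient who does not re-enrol, an event starting on the dosing day can be followed under the rule for at most 4 − 1 = 3 days. Re-enrolment is open only if no safety concern arose (Section 5.2.1), so a patient with a worrying Day 4 result is the least likely to have further study visits.

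**4. Whom does the late-lymphopenia example concern?** The SAE criterion is timed from the start of teplizumab. Per combination cohort (Section 3.3): 2 open-label patients plus 10 × 4/5 = 8 randomized to active treatment, giving 10. Two cohorts: 20 planned recipients, of up to 48 repeat-dose patients.

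**5. Does any other rule extend follow-up past completion?**
- Section 8 requires reporting of related AEs that occur after completion. It does not speak of events already open.
- Section 8.7 asks for SAE stop date and outcome, and for follow-up information to be sent within 1 calendar day of receipt. It does not require that information to be sought after completion.
- Section 8.6 extends follow-up for pregnancy only.
- Section 8.4 has a sentence on repeating an evaluation until it normalises or is explained, but it stands in the hypoglycemia paragraph.
- The SAP has no follow-up or outcome rule.

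No general rule covers an SAE or related AE that is open or first found at the last visit.

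**The case against.** The strongest reply is that Sections 8.5 and 8.8 set a minimum. Nothing forbids further follow-up, the SAE record has an outcome item, and later information must be forwarded promptly. A reader might infer that such events get no outcome at all. The documents do not support that: an outcome such as ongoing can be entered. What stands is that no final outcome is required.

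A reader might also infer that 8.8 contradicts Section 8 or the pregnancy rule. It does not. Section 8 governs reporting of new related events, pregnancy has its own forms and pathway, and all these rules can be obeyed together. They are uneven: a new related AE after completion must be reported, while a known open SAE need not be followed.

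It would likewise be too strong to say that all 8 single-dose patients have at most 3 days of event follow-up. Those who re-enrol have 12 months, and AEs are recorded from consent, so a pre-dose event can be followed for longer. The treating investigator and medical monitor also review each patient's Day 4 data before the next patient is treated. That protects the next patient but does not oblige follow-up of the one already treated.

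The gaps of 90, 270 and 304 days are calendar intervals, not estimates of the share of events affected. Day 360 is 360 − 12 = 348 days after the last planned infusion and 304 days after the last planned AG019 dose, so few new related events may be expected there. That limits the size of the problem but also keeps the fix cheap.

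Finally, the text of Section 8.10.2 and the evaluations after withheld infusions (Section 11.4.3.6) are blacked out, and Appendix B is not visible. Event-specific follow-up may exist there, so one cannot state that a patient with late lymphopenia or viral reactivation has no protocol-required follow-up of any kind. The point concerns the general rule.

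**Conclusion.** The point holds as a gap in the general follow-up rule. Follow-up of known AEs and SAEs may stop at Day 360, or at Day 4 for single-dose patients who do not re-enrol, on the day when scheduled tests may first reveal an event. Required follow-up for an event first found then is 0 days.

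A reader might infer damage to the main analysis; there is none. The primary endpoint is TEAE incidence up to 6 months (Protocol Section 10.1), the planned AE tables do not use event outcome (SAP Section 6.3.8), and a repeat-dose patient with an event open at Day 180 has 360 − 180 = 180 further days in the study. Sample size and analysis are untouched. The loss is in the description of late safety, which Section 10.1 makes a secondary endpoint, and in patient protection.

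The conclusion assumes that the protocol visit lists are complete, that no unscheduled or suspicion-triggered test intervenes, and that the unseen text contains no general rule on open events. The change is worth making because it is cheap and the study's purpose is safety; it is not critical to the validity of the results.

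**What to change.** In Section 8.8, remove study completion as an end point of SAE follow-up. In Section 8.5, remove it for AEs judged possibly, probably or definitely related to either product; it can stay for other non-serious AEs. State in both places that such events, if ongoing or first detected at the last visit, are followed until resolved, stabilised, chronic or lost to follow-up, with the outcome and its date recorded in the safety database. Any event-specific follow-up in Section 8.10.2, Section 11.4.3.6 or Appendix B should be checked for consistency with this wording.

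Cost: a protocol wording change, with a few post-study contacts for patients who have an open SAE or related AE. Treatment, the visit schedule, the sample size and the planned analyses do not change.
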